Background	Between 30-60% of older people in hospital lose muscle strength and function (deconditioning) which reduces quality of life and increases their risk of hospital readmission. Physical inactivity is estimated to cost the NHS about £1 billion per year. This can be improved with increasing physical activity and good nutrition. Our team have developed and evaluated a programme using online clinics to successfully support over 600 cancer patients living at home to stay active and eat well with provision of emotional support (SafeFit study). With many older people now using the internet for social connection, we have an opportunity to investigate whether a similar model can improve the health of older people.
Research Question/Aim(s)	Frail2Fit will explore the feasibility of training volunteers to deliver online nutrition, exercise, and behaviour change (supported self-management) to improve the health of older people after discharge from hospital. We also want to know if this supported self-management is acceptable to older people, their family members and/or carers, and the volunteers.
Study Design & Methods	In this mixed methods feasibility study, older adults in hospital and identified as frail, will be recruited from medical wards. Volunteers will be trained using our established methods to support patients to be physically active and eat well. Techniques to support behaviour change will help patients engage with the programme. Volunteers will meet the participants online over a 12-week period. We will report the number of volunteers recruited, trained, and retained. We will also report the number of patients recruited, adherence to the intervention, and any adverse events. To evaluate the benefit of the intervention we will measure participants' physical function, appetite, quality of life and well-being, and the impact on hospital admissions. To explore experiences and views about the intervention we will interview 15 patients and their family member/carers, and 10 volunteers.

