4.1 Objectives

The specific objectives include:

- 1. To develop a training programme for volunteers to support the delivery of an online multimodal intervention.
- 2. To assess the feasibility of recruiting, training and retaining volunteers to deliver the intervention.
- 3. To assess the feasibility of recruiting and retaining older adults with frailty to the trial.

4. To determine the acceptability of the intervention and explore barriers and facilitators to the intervention to support future wider implementation.

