Participants will be given the option to choose between the online intervention and telephone consultations. Participants who opt for telephone consultations will be encouraged by volunteers to perform the exercises provided in the booklet and will be given nutritional advice based on the nutrition wheel. The frequency of telephone consultations will be similar to the online intervention.

Training of volunteers

Volunteers will receive a bespoke training package adapted from the SafeFit training guidance [35]. Depending upon current Government recommendations in response to the COVID-19 pandemic the training will either be delivered online by the research team, or in-person at UHS. Once the 3 training components (i.e., exercise, nutrition, and behaviour change) have been completed, volunteers will support and shadow the trainers to deliver the intervention during the first month, aiming for 2 sessions per week to be delivered by the trainers and 1 to be delivered by the volunteers with support from the trainer. After 4 weeks, volunteers will be expected to lead the sessions independently to continue supporting participants in the adherence of the intervention with continued weekly input by the trainers.

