Volunteers will be given a training manual to help support their learning and to be used as a resource during delivery of the intervention. Volunteers will also be asked to keep an attendance record during the intervention using session completion logs and will be trained to report any adverse events.

Safety during sessions

Volunteers will be encouraged to complete a pre-session screening checklist to ensure participants are safe to exercise (e.g., safe set-up of a home exercise space; feeling well; no new or worsening symptoms). Volunteers will be taught to encourage participants to exercise at their own pace, to rest when they need to, and to move within a pain-free range of motion, ensuring that participants are working at a tailored intensity. Where possible participants will be encouraged to undertake the sessions with friends or family members present and they will be asked to keep cameras on during the

sessions. If a participant feels unwell a Zoom breakout room will enable the participant's well-being to be reviewed in private by a second volunteer.

If an emergency occurs, such as an acute medical event during the session, the volunteer will encourage participants to call their GP, or 111. If concerned about collapse, the volunteer will call 999. Volunteers will have a list of participant's addresses and GPs to hand - in case of collapse. An 'escalation plan' giving clear steps to follow, depending on the emergency situation, will be given to volunteers.

Data Collection

Participant characteristics including age, gender, domicile status, weight, body mass index, malnutrition status (MUST), baseline nutritional status (e.g., use of nutritional supplements and dietician support), co-morbidities (Charlson Co-morbidity Index) [57], cognition (Mini-mental state examination; MMSE) [58] and number of medications will be recorded. Volunteer characteristics recorded will include age, occupation, qualifications, volunteering experience, and employment status.

The primary outcome measures are feasibility and acceptability of the intervention.

Feasibility

The feasibility of implementing a volunteer-led online multi-modal intervention will be assessed by determining the number of volunteers recruited, trained and retained at the end of the study, the number of intervention sessions delivered and fidelity of volunteer delivery. Moreover, participant recruitment, retention and adherence to the intervention will be measured, as well as any adverse events

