Acceptability of the intervention

Interviews will be conducted among older adults (N= 6), volunteers (N= 6), and those involved in recruiting participants and training volunteers (N= 3), to determine the acceptability of the intervention and to explore barriers and enablers to the implementation of the intervention. Interviews will be semi-structured to help guide conversation whilst allowing participants the flexibility to elaborate and reflect on any meaningful experiences.

Older adults will be selected by purposive sampling to share their thoughts and views regarding the implementation of the volunteer-led sessions. To ensure a wide range of views are included in the interviews, participants will be selected to ensure equal distribution of male and female patients, ethnicities, and a representative age range. Interviews will also be conducted for volunteers leading the intervention. Discussions among volunteers are likely to generate a wider perspective of the implementation process and may provide insight into the group narrative on their experiences in delivering the intervention and their interaction with the research participants. Interviews will be conducted via telephone and will be audio-recorded for data collection purposes.

The interviews will be semi-structured and consist of several key open-ended questions that will help define the areas explored but allow the interviewer or interviewee to expand and diverge with the aim

of pursuing or developing an idea with more depth. The interview schedules will be underpinned by Normalisation Process Theory (NPT) (see below). The interviews will seek to explore the views of older adults, volunteers and trainers on the multi-component sessions, the barriers and facilitators to the intervention and suggestions for future implementation studies.

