- 8. What are your views on the use of trained volunteers to deliver group exercise and nutrition support to older people in the community?
 - a. Can you describe your experience with these exercise and nutrition sessions? Any advantages or disadvantages?
 - b. What was good about these groups? And what things do you think need improvement?
 - c. What were the benefits?
 - d. Were there negative experiences?
- 9. In your view, how effective were the trained volunteers at delivering the exercises and encouraging participants to be more active?
- 10. In your view, how effective were the trained volunteers at delivering the nutrition wheel and encouraging participants to eat healthily?
- 11. Do you have any suggestions or comments about the intervention?
 - a. Explore things that went well
 - b. Explore things that could be improved
- 12. What were your experiences with using the device and receiving the support online?
 - c. Explore any barriers to accessing, or using the online intervention e.g., tech knowledge, general perceptions of using technology, any misconceptions regarding online platforms, visibility and sound during sessions
 - d. Explore the things that helped / facilitated use of online tech
- 13. In your opinion, how could these volunteer-led sessions be continued and extended to other clubs?
 - c. Explore participants views on barriers and facilitators to the implementation of the intervention in other settings

Frail2Fit study

Semi-structured interview schedule for family members

- 1. Since being discharged from hospital how have things been going for your family member at home?
 - e. Could you explain what a typical day is like for them? (Build rapport and understand what life is like for them)
 - f. Explore functional capacity
 - g. Explore meaningful activities and general day to day motivation
 - h. Explore any concerns or barriers to recovery post-discharge
- 2. Tell me your views about being physically active in general.
 - e. Explore general perception on physical activity
 - f. What are the potential benefits?
 - g. Any potential harm?
- 3. In your view, what are the things/factors that could discourage older people to be more active?
 - a. Explore environmental factors, motivation, cost, accessibility, fear of injury/falls
- 4. What are the things/factors that could encourage older people to be more active?
 - c. Explore environment, social support, interest, accessibility

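### Patient interviewees for acceptability, a primary outcome, are chosen on sex, ethnicity and age alone, so first-hand reasons for stopping, low attendance or choosing the telephone may be under-represented

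*Combined protocol and SAP*

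**What the plan says.** Section 5 (Data Collection) states: "The primary outcome measures are feasibility and acceptability of the intervention". Section 5 (Study Design) says that acceptability is examined through qualitative interviews, and objective 4 in Section 4.1 reads: "To determine the acceptability of the intervention and explore barriers and facilitators to the intervention to support future wider implementation".

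The number of interviews appears twice. Section 5 (Acceptability of the intervention) has "Interviews will be conducted among older adults (N= 6), volunteers (N= 6"), plus three people involved in recruitment and training. The study summary at the front (Study Design & Methods) says "we will interview 15 patients and their family member/carers, and 10 volunteers".

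Selection of the older adults is purposive. The stated aim is "To ensure a wide range of views are included in the interviews", and the means is that "participants will be selected to ensure equal distribution of male and female patients, ethnicities, and a representative age range". No other criterion is named. Section 7.2.2 deals with recruitment to the study, not with choosing interviewees, and adds none.

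Delivery mode varies by patient choice: "Participants will be given the option to choose between the online intervention and telephone consultations" (Section 5, Intervention, repeated in Section 8.1). Section 5 also measures retention and adherence and has volunteers keep attendance logs.

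In the patient interview schedule, question 8 covers experience of the sessions, questions 9 and 10 cover how effective the volunteers were, and question 12 asks: "What were your experiences with using the device and receiving the support online". No question asks why a person stopped, missed sessions or took the telephone option.

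**The concern.** The plan aims at breadth of views but selects only on demographic features. Two patients of the same sex, ethnicity and age can differ completely in what they made of the intervention. How much they attended, whether they left, and whether they went online or used the telephone bear on this directly, and none of these is a criterion.

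Objective 4 seeks barriers as well as acceptability, and Section 4.2 uses the findings to judge suitability for a later controlled trial and for roll-out across Wessex. If the interviewees are mostly people who stayed and used the online sessions, the result leans towards acceptable. The retention figures would then show that people left without showing why.

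**Working it through.** **Step 1. What a team must do to comply.** The selection rule is met by six patients balanced on sex and ethnicity with a representative age range. Six regular online attenders can satisfy it, and nothing in the rule requires a patient who withdrew, attended little or used the telephone.

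**Step 2. Whether the schedule fills the gap.** Question 8 includes prompts on negative experiences, question 11 on improvements, and question 12 on barriers to online access. A dissatisfied attender can therefore be heard. No stem covers stopping, low attendance or choosing the telephone, and question 12 does not fit someone who received support by telephone. Section 8.2 lets participants withdraw without giving a reason, and no interview with people who withdraw is described. The volunteer data sheet has a field for reasons for leaving. None is visible in the patient data pages, although some pages are not in the public document.

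**Step 3. Size, as an illustration.** The plan derives neither interview number, so there is no figure to reproduce.

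Inputs:
- N = 23 patients (Section 7.2.1).
- n = 6 patient interviews (Section 5), or n = 15 if the study summary means 15 patients.
- k = number of the 23 who withdrew or attended little. This is an assumption, because the documents give no withdrawal or adherence rate.

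If interviewees were drawn without regard to engagement, the chance that none of the k is interviewed is

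P(none) = C(23 − k, n) / C(23, n), with C(23, 6) = 100,947 and C(23, 15) = 490,314.

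| k of 23 | n = 6 | n = 15 |
|---|---|---|
| 3 | 38,760 / 100,947 = 38% | 15,504 / 490,314 = 3.2% |
| 5 | 18,564 / 100,947 = 18% | 816 / 490,314 = 0.2% |
| 7 | 8,008 / 100,947 = 8% | 16 / 490,314 = under 0.01% |

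The same formula gives the chance of interviewing no telephone user if k counts telephone users instead.

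**Step 4. Sensitivity for n = 6.** People who disengage may be harder to recruit to interview. A simulation of 200,000 draws made them half as likely to be picked, which is a further assumption. P(none) rose from 54%, 27%, 12% and 5% to 73%, 50%, 32% and 18% for k = 2, 4, 6 and 8.

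**The case against.** The best defence is that the plan has several other ways of hearing bad news. The interviews are semi-structured and may diverge from the schedule. The patient schedule prompts for negative experiences, improvements and barriers to online access. Volunteers are asked whether the programme worked for some people and not others, and why. A family-member schedule exists, people involved in recruitment are interviewed, and retention and adherence are counted. Naming three criteria also does not forbid others.

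Much of this stands, and it rules out saying that unfavourable views would be missed entirely. It does not close the gap. The prompts help only if a disengaged patient is selected, the other informants speak second-hand, and counts carry no reasons.

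A reader might also infer that patients who withdrew or attended little are certain to be missed, because interviewees would come from people still in touch with the volunteers, and that the same applies to telephone users. The documents do not support this. They do not say that interviewees come from the volunteers' contacts, and Appendix 2 assigns the interviews to a study team member. Low attenders remain in the programme. Telephone users speak to volunteers about as often as online participants do.

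It is also fair to object that a random draw is not purposive selection, and that the result depends heavily on which interview number applies. Both points are accepted, so the probabilities serve only as illustration.

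**Conclusion.** The point holds in a limited form and is a cheap improvement. The written selection rule does not secure the range of views it promises, and the patient schedule has no question for people who stopped, attended little or chose the telephone. Their first-hand reasons may be under-represented or absent, which would tilt a primary outcome towards acceptable.

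With 6 interviews, complete omission by chance is realistic: 38% to 8% for 3 to 7 disengaged patients. If 15 patients are interviewed it is unlikely (about 3% or less), though the criteria would still not require their inclusion. These figures rest on an assumed number of disengaged patients and on selection unrelated to engagement. The conclusion about the rule and the schedule rests on the text alone.

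**What to change.** 1. Reconcile the interview numbers in the study summary and Section 5, and say whether the 15 are all patients or include family members and carers.
2. In Section 5 (Acceptability of the intervention), add attendance level, withdrawal and delivery mode to the sampling criteria alongside sex, age and ethnicity. Attendance and retention are already recorded, and delivery mode is the patient's own choice, so the team will know it.
3. Reserve some patient interviews for people who withdrew or attended little, and at least one for a telephone user, where such people exist and agree. The team should set the exact quotas.
4. Add one stem to the patient schedule, such as *What led you to stop, miss sessions or choose the telephone?*, and word question 12 so that it also fits telephone users.
5. Confirm that the consent form permits an approach for interview after sessions stop, and add this if it does not. The consent pages are not in the public document, so it may already be there.

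The cost is a few sentences, one interview question and possibly one consent line, with no extra interviews. People who withdrew are harder to reach and some will decline. With few interviews, the demographic balance may be slightly looser.

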6 STUDY SETTING

This is a single-centre feasibility study taking place at University Hospital Southampton NHS Foundation Trust. Patients on the discharge pathway will be identified and recruited from acute medical wards at UHS and volunteers will be recruited from UHS voluntary services. Volunteers will complete study training at UHS and will deliver the online intervention from UHS. Recruited older adults with frailty will participate in an online intervention from their own home upon discharge from hospital. Interviews will take place on the phone, or an online platform while participants are at home.

7 SAMPLE AND RECRUITMENT

7.1 Eligibility Criteria

Older adults with frailty discharged from UHS and volunteers from the UHS patient support hub will be invited to participate in this study (see details below).

7.1.1 Inclusion criteria

Patients:

- Older adults aged 65 years and above
- Able to provide written consent
- Discharged from UHS
- Identified as frail (Clinical Frailty Scale ≥5)
- Able to walk at least a few steps upon hospital discharge
- Able to communicate fluently enough in English

Volunteers:

Established volunteers at UHS patient support hub

- Age 16 years and above
- Completed the generic volunteer clearance and training at UHS
- Able to provide written informed consent
- Able to communicate fluently enough in English

7.1.2 Exclusion criteria

Patients:

- Older adults who are not able to safely complete the exercises included in the intervention as advised by the patient's clinician
- Patients who are discharged to rehabilitation units, or care homes
- Patients receiving end of life care

Volunteers:

 Volunteers who are unable to safely complete the exercises included in the intervention will be excluded from the study

7.2 Sampling

Participants will be recruited from UHS using purposive sampling techniques (detailed below).

7.2.1 Size of sample

Patients: A sample size of 23 participants was chosen in line with previous sample size recommendations for feasibility studies of 12-50 participants (Julious, 2005) [76, 77]. This sample size was considered an appropriate number that is pragmatic and achievable within the study timescale and resources available.

Volunteers: A sample size of 6 volunteers was chosen to provide sufficient cover to deliver the Frail2Fit intervention to groups of 5-6 older adults with 2 volunteers supporting each group.

7.2.2 Sampling technique

Purposive sampling will be applied to recruit patients on UHS acute medical wards to participate in the study, who meet the characteristics and eligibility criteria. Purposive sampling of volunteers from the UHS patient support hub will be applied to select appropriate volunteers who meet eligibility criteria for the study.

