7.3.1 Sample identification

Patients: Older adults on acute medical wards at UHS will be informed about the opportunity to participate in the study by ward staff. The clinical care team will identify eligible patients for participation in the research in line with inclusion criteria through existing access to their medical records. Ward staff will liaise closely with the research team to inform them of interested participants. Patients interested in the study will then be approached by the research team who will complete informed consent and additional screening checks to determine their suitability to participate in the study, including the clinical frailty scale (CFS).

The CFS is a judgment-based frailty tool that evaluates specific domains including comorbidity, function and cognition to generate a frailty score on a 9-point scale ranging from 1 (very fit/robust and active) to 9 (terminally ill) [78]. The CFS is a valid and reliable measure of frailty in older people and is associated with a range of clinical outcomes including comorbidity, falls, cognition, function, and mortality [79]. Patients scoring ≥5 on CFS will be eligible to participate in the study.

Volunteers: Volunteers will be identified by hospital voluntary services within the UHS patient support hub, managed by [name]. The patient support hub helps ensure patients with a range of needs are supported in their own homes following discharge from hospital, including providing food parcels, and befriending services. The patient support hub recruits volunteers with an interest in supporting patients post-discharge with practical and emotional support. The research team will liaise closely with the patient support hub in the recruitment and support of volunteers interested in participating in the Frail2Fit study. The support hub team will identify and approach existing patient support hub volunteers to invite them to the study. All volunteers associated with the support hub will have appropriate clearance and training from UHS. Interested volunteers will be approached by the research team with a participant information sheet and if they meet eligibility criteria (i.e., no contraindications to the exercise component) they will complete informed consent. Two volunteers will be matched based upon volunteer experience levels to deliver the Frail2Fit intervention to a group of 5-6 participants (i.e., any newer volunteers will be matched with experienced support hub volunteers).

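### Patient recruitment is part of the primary outcome, but the plan counts no eligible, approached or declining patients, and the cohort is sampled purposively on unnamed characteristics

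*Combined protocol and SAP*

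**What the plan says.** Section 7.2 applies purposive sampling to participants generally, and section 7.2.2 applies it to the main patient cohort: "Purposive sampling will be applied to recruit patients on UHS acute medical wards to participate in the study". It ties the choice to patients' characteristics and the eligibility criteria, but lists no characteristics, quotas or preferences.

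Section 7.3.1 sets out the route into the study. Identification is from medical records: "The clinical care team will identify eligible patients for participation in the research in line with inclusion criteria". Then "Ward staff will liaise closely with the research team to inform them of interested participants", and "Patients interested in the study will then be approached by the research team who will complete informed consent and additional screening checks", the Clinical Frailty Scale among them. Section 7.3.2 repeats that the research team is told of interested patients.

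Objective 3 in section 4.1 is "To assess the feasibility of recruiting and retaining older adults with frailty to the trial". In section 5, under Data Collection, "The primary outcome measures are feasibility and acceptability of the intervention". Under Feasibility, "participant recruitment, retention and adherence to the intervention will be measured, as well as any adverse events". The study summary promises the number of patients recruited. The quantitative analysis text in section 5 names volunteer counts and patients' adherence, but not patient recruitment or retention.

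The interviews have their own purposive sample (section 5, Acceptability of the intervention): "Older adults will be selected by purposive sampling to share their thoughts and views". There the selection factors are named: sex, ethnicity and age.

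**The concern.** Purposive sampling suits the interviews, where a spread of views is the aim. A recruitment question is different: it asks what fraction of the patients who could take part do take part. That needs a count of those patients, and the plan describes none. The research team first meets patients after interest has been expressed, so anyone not told, not interested or declining at ward level leaves no trace in the study data.

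The number recruited does not fill the gap. The target of 23 is fixed in advance, so reaching it says little about how many eligible patients had to be found. Section 4.2 intends the study to inform a controlled trial and a wider roll-out, and both need that figure. Retention and adherence are affected differently: they can be calculated, but without a record of how the cohort arose the reader cannot judge to whom they apply.

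**Working it through.** **The plan's own figure.** The patient sample size is 23 (section 7.2.1), justified by a recommended range of 12 to 50 and by pragmatism. 23 lies in that range. There is no alpha, power or precision target, so there is no calculation to reproduce.

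**Which measures have a denominator?**

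| Measure | Denominator in the plan | Computable as written? |
|---|---|---|
| Uptake among eligible patients | none planned | no |
| Uptake among approached patients | none planned | no |
| Consent among interested patients | interested patients passed on by ward staff | possibly, if the team counts them |
| Retention | patients enrolled (target 23) | yes |
| Adherence | maximum sessions: 3×4 + 2×4 + 1×4 = 24 | yes |

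As examples with assumed counts, retention of 18/23 is 78.3% (exact 95% CI 56.3 to 92.5%) and 16/23 is 69.6% (47.1 to 86.8%). Neither needs an eligible count.

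**How much does the missing count matter for recruitment?** The documents give no eligible count, so the denominators here are assumptions. The intervals are Clopper-Pearson: for x of n, the lower limit is the 0.025 quantile of Beta(x, n−x+1) and the upper limit the 0.975 quantile of Beta(x+1, n−x).

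| Assumed eligible | 23/eligible | Exact 95% CI |
|---|---|---|
| 30 | 76.7% | 57.7 to 90.1% |
| 60 | 38.3% | 26.1 to 51.8% |
| 100 | 23.0% | 15.2 to 32.5% |
| 200 | 11.5% | 7.4 to 16.8% |

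**What would the interested-patient figure hide?** If all eligible patients are informed, uptake = s × c, where s is the share interested and c the share of interested patients who enrol. Only c could be seen by the research team. Take c = 70% (assumed), so that about 33 interested patients give 23 recruits:

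| Assumed s | Uptake s × 0.70 | Eligible needed, 23/(s × 0.70), rounded up |
|---|---|---|
| 20% | 14% | 165 |
| 40% | 28% | 83 |
| 60% | 42% | 55 |
| 80% | 56% | 42 |

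An observed 70% is therefore compatible with a fourfold range of uptake. With c between 50% and 90% and s between 20% and 80%, uptake runs from 0.2 × 0.5 = 10% to 0.8 × 0.9 = 72%.

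**The case against.** The strongest reply is that purposive sampling is not what removes the denominator. An unrecorded count is, and since the care team already works from records, a log alone would supply it. That is right about the cause, and the log is the essential part of the fix. But a log only records selection. While section 7.2.2 allows choice on unnamed characteristics, the group approached remains undefined.

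A second reply is that the label may be loose. Section 7.3 says eligible patients are identified and first approached by their care team, and 7.3.1 ties identification to the inclusion criteria, which could simply mean criterion-based recruitment. That is a fair reading. If it is the intended one, stating it costs nothing.

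A reader might go further and infer that ward staff will pick patients likely to cope with online sessions, so that recruitment, retention and adherence come out too high. The documents do not support this. Selective approach is possible under the wording but is not described. The preloaded tablets, ward teaching and digital support (section 5, Digital training) and the telephone option weaken any reason to select on digital skill.

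It is also said that planning needs mainly recruits per ward per month, which follows from the number recruited together with dates and wards. That helps at this hospital. It does not carry over to wards with a different flow of eligible patients.

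Finally, the Background cites a busy clinical environment as a barrier in the team's earlier ward study, so the work for ward staff should be kept small. The study flow chart is also not visible in the available text, and a screening count there cannot be ruled out.

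**Conclusion.** The point holds for recruitment. On the visible text, the study can report how many patients were recruited and possibly the share of interested patients who consented, but not uptake among those eligible or approached. The recruiting half of Objective 3, which is part of the primary outcome, therefore cannot be answered beyond a count near a preset target. On assumed eligible counts of 30 to 200, the same 23 recruits mean anything from 77% to 12%.

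It does not hold that retention and adherence lack denominators, though a reader might infer it. They have the patients enrolled and 24 sessions. For these two the limit is generalisability: they describe a group whose selection is not recorded, with no direction of bias shown.

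Nor do the documents support any single inflation factor. If 100 patients were eligible and 30 interested, the consent share among interested patients would be 100/30 = 3.3 times uptake among eligible patients. With 46 eligible, all told, it would be 46/30 = 1.5 times. Both rest wholly on assumed counts.

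**What to change.** 1. **Section 7.3.1:** add an anonymous screening log, kept as the care team identifies patients from records. Count patients eligible, approached, interested and consented, with the reason for not proceeding where offered. The research team's checks, including the frailty score, come after interest, so ineligibility found at that stage should be logged as its own reason.
2. **Section 5, Feasibility and quantitative analysis:** define recruitment as consented/eligible and consented/approached, with eligible meaning as identified by the care team. Report each with an exact 95% CI, and list patient recruitment and retention among the descriptive analyses.
3. **Sections 7.2 and 7.2.2, patients only:** replace purposive sampling with approach of all patients who meet the criteria on participating wards on recruiting days. Keep purposive sampling for the interviews.

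The cost is some wording and a little ward-staff or research-team time per eligible patient; having the research team hold the log would limit the burden on wards. The reported uptake may be less favourable. The log has to start with recruitment, because the counts cannot be reliably rebuilt afterwards.
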